4.3. Screening/ Baseline Failures

Screen failures are defined as subjects who consent to participate in the study but are never subsequently randomized. In order to ensure transparent reporting of screen failure subjects, a minimal set of screen failure information is required including Demography, Screen Failure details, Eligibility Criteria, and any Serious Adverse Events (SAEs). Re-screening of subjects will not be allowed in this study.

4.4. Withdrawal/ Stopping Criteria

A subject may withdraw from the study at any time at his/her own request, or may be withdrawn at any time at the discretion of the investigator for safety, behavioural or administrative reasons.

If the reason for removal of a subject from the study is an AE or an abnormal laboratory test result, the principal specific event or test will be recorded on the electronic Case Report Form (eCRF). If a subject is withdrawn from the study because of a product limiting AE, thorough efforts should be clearly made to document the outcome. Any AEs ongoing at the final visit will be followed up until resolved, the condition stabilizes, is otherwise explained, or the subject is lost to follow-up.

The following actions must be taken in relation to a subject who fails to attend the clinic for a required study visit:

- The site must attempt to contact the subject and re-schedule the missed visit as soon as possible.

 GlaxoSmithKline	Document Name	090032d580e2d8a6 20 Day Cream.doc		
	Type	Version	Document Identifier	Effective Date
	eldo_controlled	0.0; CURRENT Effective Date: CURRENT	090032d580e2d8a6	07-Jun-2017 01:32:30
	Reason For Issue	Auto Issue		

- The site must counsel the subject on the importance of maintaining the assigned visit schedule and ascertain whether or not the subject wishes to and/or should continue in the study.
- In cases where the subject is deemed ‘lost to follow up’, the investigator or designee must make every effort to regain contact with the subject (where possible, at least 2 telephone calls). The contact attempt should be documented in the subject’s record.
- Should the subject continue to be unreachable, only then will he/she be considered to have withdrawn from the study with a primary reason of “Lost to Follow-up”.

4.5. Subject Replacement

Subjects who withdraw from the study post-randomization will not be replaced.

4.6. Subject and Study Completion

A completed subject is one who has completed all phases of the study.

The end of the study is defined as the date of the last subject’s last visit.

 GlaxoSmithKline	Document Name	Gsk200723721308F 20 Day Cream.doc		
	Type	Version	Document Identifier	Effective Date
	eldo_controlled	0.0; CURRENT/Effective/Current	090032d580e2d816	07-Jun-2017 01:32:30
	Reason For Issue	Auto Issue		

5. PRODUCT INFORMATION

5.1. Study Product

The following study products will be supplied by the Clinical Supplies Department, GSKCH:

	Reference / Washout Cleanser	Test Product	Reference / Washout Sunscreen
Product Name	Simple™ Kind to Skin Moisturising Facial Wash	Physiogel Calming Relief SPF 20 Cream	Sunmax Sensitive SPF 50
Product Formulation Code	N/A (Commercial, UK)	CCI [REDACTED]	CCI [REDACTED]
Application Quantity	Approximately 0.6-1 g		
Route of Application	Topical		
Application Instructions	
In your hands, work a small amount into a lather. Massage onto wet skin, rinse with water.
 
Avoid contact with eyes. If contact occurs, rinse thoroughly with water.
 
Apply twice a day (morning and evening)
	
Dispense two pumps of product onto the fingertips and apply to the full face.
 
Avoid contact with eyes. If contact occurs rinse thoroughly with water.
 
Apply twice a day (morning and evening)
 
Do not apply in the morning if you are visiting the site on the same day.
	
Dispense a pea-sized quantity onto the fingertips and apply to the full face.
 
Avoid contact with eyes. If contact occurs rinse thoroughly with water.
 
Apply twice a day (morning and lunchtime)
 
Do not apply in the morning if you are visiting the site on the same day.

 GlaxoSmithKline	Document Name	GSK-207207-01-01-01F 20 Day Cream.doc		
	Type	Version	Document Identifier	Effective Date
	eldo_controlled	0.0: Current Effective Date: Current	090032d580e2d8a6	07-Jun-2017 01:32:30
	Reason For Issue	Auto Issue		

Upon completion of the washout phase, subjects considered to be eligible for the test phase will be randomised to two groups (Group 1: Test product; Group 2: No-treatment) and a qualified dermatologist with experience administering facial peels will conduct the 70% Glycolic Acid procedure.

Subjects randomised to Group 1 will be instructed to apply the test product twice-daily (morning and evening) after cleansing, for a total of 14 consecutive days. All subjects will be instructed to continue using the facial cleanser twice-daily during the morning and evening, and to apply the sunscreen in the morning and at lunchtime. A summary of the subject's post-randomization regimen is included below for clarity.

Randomized Group	Morning	Lunchtime*	Evening
Group 1	1. Cleansing 2. Test Product 3. Sunscreen	2. Sunscreen	1. Cleansing 2. Test Product
Group 2	1. Cleansing 2. Sunscreen	2. Sunscreen	2. Cleansing

*Lunchtime application must be at least 3 hours after previous sunscreen application

Subjects will not apply any sunscreen on the day of the facial peel procedure (Day 8), since they will remain at site until the evening (after 5 pm). On the morning of each visit, prior to arriving to the test site, subjects will be instructed to cleanse their face and not to apply any test product or sunscreen until after all measurements and assessments have been completed. Before leaving the site, subjects will undergo test product and/or sunscreen application under supervision. After leaving the site, subjects should apply the sunscreen a second time, but no sooner than 3 hours after the previous application.

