Image capture (VISIA) Post-Procedure, Post-Treatment ¹⁴				X				X
Subject Self-Assessment Post-Procedure, Post-Treatment ¹⁵			X	X	X	X	X	X
Subject Global Self-Assessment								X
Dermatologist Assessment Post-Procedure, Post-Treatment ¹⁵			X	X	X	X	X	X
Dermatologist Global Assessment of Tolerance								X
Supervised Test-Product Application ¹⁶				X	X	X	X	
Supervised Sunscreen Application ¹⁷				X	X	X	X	
Products and Test Diary Return								X
Discharge from Study								X

	Document Name	Post 207213721308F 20 Day Cream.doc		
	Type	Version	Document Identifier	Effective Date
	eldo controlled	0.0; CURRENT/Effective/Current	090032d580e2d8#6	07-Jun-2017 01:32:30
	Reason For Issue	Auto Issue		

1. For Visits 3-8, subjects will be instructed to cleanse their face at home using the cleanser provided and must not use any other product on their face, including the test product (Group I only) and sunscreen. Subjects will be instructed to bring the dispensed cleanser, sunscreen and test product (Group I only) with them to all visits. Subjects will be invited to the site in the morning (prior to 9 am) to avoid exposure to strong sunlight.
2. The Investigator or designee will review the diary to monitor and encourage compliance. Additional or missed product applications will be recorded as deviations. The Evaluator must be blind to diary review.
3. Exclusion Criteria 9 will not be included for this assessment. Exclusion criteria 9 is evaluated based on the results from the sensitivity test.
4. To include a review of the inclusion/exclusion criteria specified in Appendix 4. Subjects must be considered compliant with these inclusion/exclusion criteria in order to remain eligible for the study.
5. Peel regimen (70% Glycolic Acid facial peel solution, Bicarbonate Neutralizing Solution and Sunmax Sensitive SPF 50) to be applied to the volar forearm of each subject by a qualified dermatologist.
6. Assessments to be taken 45±15 minutes after completion of the study material sensitivity test.
7. Assessments to be taken 24±4 hours after completion of the study material sensitivity test.
8. Assessments to be taken 7 days after completion of the study material sensitivity test.
9. 70% Glycolic Acid facial peel to be administered by a qualified dermatologist who must be blind to randomization. The Glycolic Acid treatment and neutralizing solution will be sourced commercially by the study site.
10. Assessments to be taken 60±15 minutes after completion of the facial peel procedure.

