10. Dermatologist Assessment Post-Procedure, Post-Treatment*
11. Supervised Test-Product Application
12. Supervised Sunscreen Application

* Assessments to be taken 24±4 hours after completion of the facial peel procedure

Visit 5 / Day 10 (1 Day after Visit 4); Visit 6 / Day 11 (1 Day after Visit 5), Visit 7 / Day 15 (4 Days After Visit 6)

The following assessments will be conducted in the order written:

1. Current / Concomitant Medication
2. Adverse Events
3. Continued Subject Eligibility
4. Compliance (Diary review)
5. Washout Products Weighing
6. Test Product Weighing
7. Instrumental Measurements Post-Procedure, Post-Treatment*
8. Subject Self-Assessment Post-Procedure, Post-Treatment*
9. Dermatologist Assessment Post-Procedure, Post-Treatment*
10. Supervised Test-Product Application
11. Supervised Sunscreen Application

* Assessments to be taken 48±4 (Visit 5), 72±4 (Visit 6) and 168±4 (Visit 7) hours after completion of the facial peel procedure

Visit 8 / Day 22 (7 Days after Visit 7)

The following assessments will be conducted in the order written:

1. Current / Concomitant Medication
2. Adverse Events
3. Continued Subject Eligibility
4. Compliance (Diary review)
5. Washout Products Weighing
6. Test Product Weighing

 GlaxoSmithKline	Document Name	PhysiGel Calming Relief SPF 20 Day Cream.doc		
	Type	Version	Document Identifier	Effective Date
	eldo_controlled	0.0; CURRENT Effective Date: CURRENT	090032d580e2d8a6	07-Jun-2017 01:32:30
	Reason For Issue	Auto Issue		

 7. Instrumental Measurements Post-Procedure, Post-Treatment* 8. Image capture (VISIA) Post-Procedure, Post-Treatment* 9. Subject Self-Assessment Post-Procedure, Post-Treatment* 10. Subject Global Self-Assessment 11. Dermatologist Assessment Post-Procedure, Post-Treatment* 12. Dermatologist Global Assessment of Tolerance 13. Products and Test Diary Return 14. Discharge from Study 
* Assessments to be taken 336±4 hours after completion of the facial peel procedure

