3.2. Subject Restrictions

Lifestyle/ Dietary

During the entire study (screening – Last-Subject, Last-Visit (LSLV));
 
 1. Not to participate in any other cosmetic or therapeutic study 2. Not to add any new cosmetic product to their current personal care regimen (e.g. shampoo, shower gel, hand soap) or switch brands of laundry products during the study
Medications and Treatments

On the day of site visit;
 
 1. Not to apply any detergents (e.g. soaps, shampoos, bath and shower products) to their face other than the cleanser provided (Simple Kind to Skin Moisturising Facial Wash) 2. Not to apply any leave-on cosmetics (e.g. creams, lotions, oily cleansing products, mascara) including the test product (PhysiGel Calming Relief SPF 20 Cream) and sunscreen (Sunmax Sensitive SPF 50) to their face or eyelashes 3. Not to consume any caffeine 4. Not to smoke (includes cigarettes, shisha, cigars)

During the entire study (screening – LSLV);
 
 1. Not to apply any detergents (e.g. soaps, shampoos, bath and shower products) to their face other than the cleanser provided (Simple Kind to Skin Moisturising Facial Wash) 2. Not to use any facial skin treatments or cosmetic products other than the products provided for this study. Subjects are permitted to wear their usual mascara during this study 3. Not to use any study prohibited medication as specified in the exclusion criteria, including anti-inflammatory, analgesic or photosensitizing treatments 4. To avoid direct exposure to sunlight by seeking the shade and to wear a sun hat and sunglasses when outside as far as practically possible

 GlaxoSmithKline	Document Name	Physiogel Calming Relief SPF 20 Day Cream.doc		
	Type	Version	Document Identifier	Effective Date
	eldo_controlled	0.0; CURRENT Effective Date: CURRENT	090032d580e2d8a6	07-Jun-2017 01:32:30
	Reason For Issue	Auto Issue		

5. To avoid ultraviolet (UV) treatments and tanning salons
6. Female subjects of child-bearing potential must use effective contraception
7. Subjects must not change any hormonal treatment or contraception that they may be receiving and must have used the same contraception for 3 months prior to screening
8. Subjects must not undergo any aesthetic, cosmetic or dermatological treatment in the treatment area (face or eyes)
9. Use of facial scrubs, depilatory creams, waxing, bleaching, microdermabrasion, and laser hair removal

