3.4. Study Design and Dose Justification

This study is a randomized, evaluator-blind, single-center and two-arm clinical study designed to evaluate the local tolerance and cosmetic efficacy of a topical skin care formulation in healthy female subjects with moderate to advanced photo-damaged facial skin who have undergone a 70% Glycolic Acid facial peel procedure. Glycolic acid is selected due to its widespread use and favourable tolerance profile. [Sharad]

The test product (Physiogel Calming Relief SPF 20 Cream) is designed for subjects with dry, irritated skin and there is favourable local tolerance clinical data to support its use for application to sensitive, post-procedure skin. The test product will be applied twice daily, as consistent with the marketed instructions for use.

A 7 day washout phase is included to standardize subjects' skin care regimens. Subjects will be provided with a commercially available facial cleanser (Simple Kind

Document Name	Protocol 2017-01-08F 20 Day Cream.doc		
Type	Version	Document Identifier	Effective Date
eldo_controlled	0.0: Current Effective/Current	090032d580e2d8a6	07-Jun-2017 01:32:30
Reason For Issue	Auto Issue		

	2. Sunscreen		
--	--------------	--	--

*Lunchtime application must be at least 3 hours after previous sunscreen application

Subjects will not apply any sunscreen on the day of the facial peel procedure (Day 8), since they will remain at site until the evening (after 5 pm). On the morning of each visit, prior to arriving at the site, subjects will be instructed to cleanse their face and not to apply any test product or sunscreen until after all measurements and assessments have been completed. Before leaving the site, subjects will undergo supervised test product and/or sunscreen application. After leaving the site, subjects should apply the sunscreen a second time, but no sooner than 3 hours after the previous application.

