6.4.12. Supervised Sunscreen Application

All subjects will undergo supervised sunscreen application. The Investigator or designee will oversee application of the SPF 50 sunscreen. Product application will be recorded on the eCRF and subject diary.

6.5. Visit 5 – 1 day after Visit 4

Subjects will be instructed to arrive at the site prior to 9:00 AM to minimize exposure to intense sunlight.

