6.7.11. Supervised Sunscreen Application

All subjects will undergo supervised sunscreen application. The Investigator or designee will oversee application of the SPF 50 sunscreen. Product application will be recorded on the eCRF and subject diary.

6.8. Visit 8 – 7 days after Visit 7

Subjects will be instructed to arrive at the site prior to 9:00 AM to minimize exposure to intense sunlight.

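### Sunscreen is withheld on the morning of Visit 8, and the Visit 8 procedures omit the supervised application that the general text promises before subjects leave

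*Protocol*

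**What the plan says.** **Withholding.** The sunscreen instructions in Protocol section 5.1 read: "Do not apply in the morning if you are visiting the site on the same day". Section 3.2 bars leave-on products on the day of a site visit, with the test product "and sunscreen (Sunmax Sensitive SPF 50) to their face or eyelashes" expressly included. Footnote 1 of the Schedule of Events, which applies to Visits 3 to 8, says subjects "must not use any other product on their face, including the test product (Group I only) and sunscreen".

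**Restoring, general text.** Section 5, below the regimen table, postpones test product and sunscreen on each visit morning until the assessments are finished. It continues: "Before leaving the site, subjects will undergo test product and/or sunscreen application under supervision". Section 3.4 has the same rule: "Before leaving the site, subjects will undergo supervised test product and/or sunscreen application". Both then ask for a second sunscreen application at least 3 hours after the first. In the text available, the only exception stated is the peel day (Day 8).

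**Restoring, visit-level text.** Section 6.4.12 (Visit 4) says "All subjects will undergo supervised sunscreen application", and sections 6.5.11, 6.6.11 and 6.7.11 repeat the step for Visits 5 to 7. The Schedule and SAP Appendix 1 mark it at Visits 4 to 7 only. The Visit 8 list in section 3.1 ends: "12. Dermatologist Global Assessment of Tolerance 13. Products and Test Diary Return 14. Discharge from Study". The synopsis list ends the same way, and section 6.8 has no application step. Section 6.8.13 has the washout products returned, and section 5.1 classes the SPF 50 sunscreen as one of them.

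**The concern.** The study asks subjects to arrive at Visit 8 without sunscreen, and for Group 1 also without the SPF 20 test cream. The general text says sunscreen is put back before they leave. The detailed Visit 8 procedures, which site staff will work from, do not include it and then collect the product. The later second application is also impossible with study sunscreen once it has been handed in.

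What is at stake is sun protection for one day. The Protocol's introduction says sunscreen helps protect skin while it heals, and it lists transient post-inflammatory hyperpigmentation among the minor side effects of the peel. No endpoint, hypothesis test or sample-size figure depends on this.

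**Working it through.** The plan gives no figure on this point to reproduce. The check sets the texts side by side, followed by three small counts.

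**1. Visits from the peel day onward**

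| Visit | Sunscreen on arrival | Visit-level safeguard before leaving | Sunscreen kept afterwards |
|---|---|---|---|
| 3 (Day 8) | Withheld | Stay on site until at least 5 PM (6.3.25) | Yes |
| 4, 5, 6, 7 | Withheld | Supervised application (6.4.12, 6.5.11, 6.6.11, 6.7.11) | Yes |
| 8 (Day 22) | Withheld | None in the Schedule, either list, 6.8 or SAP Appendix 1 | No (6.8.13) |

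Of the 5 visits after the peel day, sunscreen is withheld at 5. The visit-level procedures restore it at 4. The gap is 5 − 4 = 1 visit, or one application per subject. Planned completers number about 60, with 80 randomised.

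**2. Can subjects leave Visit 8 in daytime?** Section 6.8 says: "Subjects will be instructed to arrive at the site prior to 9:00 AM to minimize exposure to intense sunlight". No minimum stay or departure time is given. I assume the peel ended between 09:00 and 11:00 on Day 8: footnote 1 has arrival before 9 am, and 11:00 + 360 min = 17:00. Since 336 h is exactly 14 days, the ±4 h window on Day 22 is:

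- peel ended 09:00: 05:00 to 13:00
- peel ended 11:00: 07:00 to 15:00

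Assessments therefore finish by 13:00 to 15:00 at the latest, so departure can fall in daytime across the whole range.

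**3. What an added Day 22 application does to the compliance rule.** Section 5.4 sets the threshold at 80% of instructed applications after the peel but does not state how many there are. My count uses two sunscreen applications a day from Day 9:

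- none on Day 22: 13 × 2 = 26; 0.8 × 26 = 20.8, so at least 21
- one supervised application on Day 22: 26 + 1 = 27; 0.8 × 27 = 21.6, so at least 22
- general text followed in full on Day 22: 14 × 2 = 28; 0.8 × 28 = 22.4, so at least 23

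The existing conflict thus already leaves the denominator open (26 or 28), and an added step would make it 27 unless section 5.4 says otherwise.

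**4. What it does to the adverse event window.** Section 7.2 collects events until 5 days after the last study product. Section 5.1 lists the cleanser as a study product, and footnote 1 has it used on the morning of Day 22. On that reading the window ends on Day 22 + 5 = Day 27, with or without the new step. Protocol 9.2.1 and SAP 5.1, however, define test-phase product as test product in Group 1 and sunscreen in Group 2. If that definition were carried over, the last product day would be Day 21 and the window would end on Day 26. A Day 22 sunscreen application would then move it to Day 27 in Group 2 only.

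**The case against.** **The general text already covers Visit 8.** Sections 3.4 and 5 speak of each visit, and read literally they restore sunscreen at Visit 8 before discharge. This stands. A reader might infer that the plan makes no provision at all for sunscreen at Visit 8, but the documents do not support that. They show a general rule with no matching step in the Visit 8 procedures.

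**The omission may be a deliberate end of treatment.** Test product is used for 14 consecutive days, which counted from Day 8 ends on Day 21. All visit-level sources agree with one another, and Visit 8 collects everything and discharges the subject. This explains why no test product is applied. It does not explain withholding sunscreen that same morning, or why the general text makes no exception. On Day 8, the other visit without sunscreen, the Protocol supplies an alternative by keeping subjects on site.

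**The safety rationale is thin by Day 22.** The introduction's remarks on sunscreen belong to a passage that opens with the period immediately after the procedure. The peel is classed as superficial, and barrier function is expected to be normal within 24 to 48 hours (3.4). The shade-and-hat rule runs to the end of the study (3.2), and exclusion criterion 8 removes people planning long periods outdoors. All of this stands and keeps the point very minor.

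**The fix has side effects and costs.** This also stands. The compliance and adverse event rules need a sentence each, and the change needs an eCRF field and amendments to both documents.

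**Conclusion.** The concern holds as a conflict between the general text in sections 3.4 and 5 and the Visit 8 procedures. A site that follows the procedures would send subjects home in daytime without sunscreen they had left off at the study's instruction. The size is one application on one day, for about 60 planned completers, 14 days after a superficial peel. It is a cheap improvement of very low importance.

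Two stronger inferences are not supported. The first is that results are at risk: no endpoint depends on sunscreen applied after the Visit 8 assessments. The second is that harm is likely: the documents give no figure for the risk from one missed application at two weeks, and they list several mitigating measures.

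The conclusion rests on the assumed peel time for daytime departure, on my own count of instructed applications, and on the available text of section 3.4, which is incomplete in the copy reviewed.

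**What to change.** - **Add the step.** Insert a supervised sunscreen application for all subjects at Visit 8 between step 12 (Dermatologist global assessment) and step 13 (product and diary return). Make the change in the Schedule of Events, both Visit 8 lists, section 6.8 and SAP Appendix 1.
- **Align the general text.** In sections 3.4 and 5, limit the test-product application and the second sunscreen application to Visits 4 to 7. The Day 8 test-product application is already governed by section 6.3.22.
- **Section 5.4.** State that the Day 22 application is not counted in the 80% compliance denominator.
- **Section 7.2.** State that the Day 22 application does not extend the adverse event window.

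The cost is a few minutes per subject, one eCRF field, and a minor amendment to the Protocol and the SAP (already at final version 2.0), with ethics committee submission where the country requires it. The product is already on site, because subjects bring it to every visit. The weighings, the diary review and all assessments at Visit 8 come before the new step, so no measurement changes.
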